## **A. Benefit to Society and Purpose**

Current state-of-the-art treatments for posttraumatic stress disorder (PTSD) are lacking in efficacy. There are two main evidence-based psychological treatments for PTSD. Prolonged Exposure (Foa et al. 1991) (PE) is a largely-exposure based intervention that has been found efficacious for the reduction of PTSD symptoms (Foa, Rothbaum, Riggs, & Murdock 1991; Schnurr et al. 2007); however, PE is associated with post-treatment remission rates of only ~53-60% (Foa et al. 1999; Resick et al. 2002; Schnurr, Friedman, Engel, Foa, Shea, Chow, Resick, Thurston, Orsillo, Haug, Turner, & Bernardy 2007). Cognitive Processing Therapy (CPT) (Resick and Schnicke 1992) is also a widely studied and efficacious psychological treatment for PTSD, which focuses both on exposure to the trauma memory as well as cognitive therapy techniques. As with PE, post-treatment remission rates for CPT are only ~53-60% (Monson et al. 2006; Resick, Nishith, Weaver, Astin, & Feuer 2002; Resick et al. 2008) thus also indicating need for improvement in overall efficacy and consistency of response across individuals.

Repeated exposure to the trauma memory (RETM) in a safe context is a therapeutic intervention common to both PE and CPT (though implemented differently in PE and CPT). RETM is based on a fear extinction model (Foa, Rothbaum, Riggs, & Murdock 1991; Foa and Kozak 1986; Rothbaum and Davis 2003): the memory of the trauma is conceptualized as a conditioned stimulus (CS+) that triggers anxiety responses (conditioned responses) due to its association with the traumatic event (i.e., the unconditioned stimulus). Repeated exposure to the traumatic memory (CS+) in a safe context is theorized to weaken the predictive value of the CS+ and thereby weaken the ability of the traumatic memory or reminders to elicit marked distress.

Extensive research on the neural mechanisms mediating fear extinction suggests that fear extinction is mediated largely by the functional interaction between three separate neural structures (Milad et al. 2007; Myers and Davis 2007; Phelps et al. 2004; Sotres-Bayon et al. 2006). First, the amygdala is critical for the detection of the CS+ and motivating the expression of fear-relevant behavioral responding. Second, the hippocampus is involved in contextual modulation of amygdala processing in the presence of the CS+. Third, the medial prefrontal cortex (mPFC) has direct anatomical projections to the amygdala (Ghashghaei et al. 2007) and is critical for down-regulation of amygdala response. Finally, these neural mechanisms mediating fear extinction overlap with the neural circuitry known to be altered in PTSD (Rauch et al. 2006; Shin et al. 2006).

Basic research also demonstrates that fear extinction learning involves formation of a new memory, not the erasure of an old memory (Bouton 2002; Bouton 2004; Craske et al. 2008; Craske et al. 2014). Fear responding during subsequent presentations of the CS+ is determined by the degree of competition between the new (safe) memory and the old (danger) memory. For example, context renewal refers to recovered fear responding after fear extinction learning by placing the organism in a different context than where the extinction learning occurred (Bouton 2002; Bouton 2004). Thus, efforts have been devoted to enhancing the consolidation of the new (safe) memory (Davis et al. 2006; Walker and Davis 1997) in order to

boost its subsequent recall across contexts and thereby decrease fear responding upon future presentations of the CS+ in new contexts.

There is emerging research demonstrating that dopamine is critical to the consolidation and subsequent recall of fear extinction learning (Abraham et al. 2012; Haaker et al. 2013a; Hikind and Maroun 2008; Mueller et al. 2010). Rodent studies have demonstrated that dopamine antagonists delivered after fear extinction training lead to *increased* fear responding upon subsequent CS+ presentation, and that dopamine agonists delivered after fear extinction training lead to *decreased* fear responding upon subsequent CS+ presentations. Similarly, a recent study of healthy adult humans demonstrated that oral administration of 150 mg L-DOPA after fear extinction learning led to decreased fear responding, even when tested in a new context. Further, this study also found that resting-state functional connectivity, measured ~45 minutes after post-extinction learning L-DOPA administration, between the ventral tegmental area (VTA) and mPFC was correlated with magnitude of mPFC recruitment during recall of the fear extinction learning. This latter finding suggests that the mechanism by which L-DOPA boosts consolidation of fear extinction learning is through acutely reorganized dopaminergic resting-state networks. Indeed, other studies have demonstrated an acute effect of L-DOPA administration on resting-state functional connectivity within dopaminergic neural networks (Cole et al. 2013a; Cole et al. 2013b; Kelly et al. 2009). Thus, agents that increase dopamine transmission acutely during the post-extinction learning consolidation window, and thereby acutely altering organization of dopaminergic neural networks, show promise for boosting the consolidation of fear extinction memories and decreasing fear responding. It is well established that dopamine neurotransmission demonstrates a nonlinear inverted “U” shaped relationship with measures of performance (Cools and D’Esposito 2011). This line of research demonstrates an optimal level of dopamine neurotransmission, varying by the task, for achieving optimal performance. Similarly, human studies using L-DOPA demonstrate an inverted “U” shaped relationship between L-DOPA dose and measures of performance (Monte-Silva et al. 2010; Thirugnanasambandam et al. 2011).

Genetic variation is a primary contributor to individual differences in baseline dopamine neurotransmission (Cools & D’Esposito 2011; Frank and Fossella 2011). Individuals with specific alleles in genes coding for high baseline dopamine demonstrate better performance on tasks probing working memory, cognitive control, and social cognition (Diamond et al. 2004; Egan et al. 2001; Meyer-Lindenberg et al. 2005). Genetic variants in baseline dopamine neurotransmission would therefore be expected to modulate performance-enhancing effects of L-DOPA, such that individuals with low endogenous would be expected to have increased performance upon exogenously increasing dopamine neurotransmission; whereas individuals with high endogenous dopamine would be expected to have performance deteriorate from exogenously increasing dopamine neurotransmission. In support of this hypothesis, a recent study found an interaction between L-DOPA administration and endogenous dopamine neurotransmission (as indicated by a polygenic score pooled across COMT, DAT, DRD1-3) on motor learning performance, such that individuals with a combination of alleles coding for higher baseline dopamine demonstrated a weaker learning benefit from L-DOPA, whereas individuals

**PI:** [name].

with a combination of alleles coding for lower baseline dopamine demonstrated a stronger learning benefit from L-DOPA (Pearson-Fuhrhop et al. 2013). These data demonstrate the non-linear relationship between performance and dopamine levels, suggesting that any investigation of potential effects of boosting dopamine neurotransmission as a means of boosting learning needs to account for baseline dopamine neurotransmission.

Overall, the proposed project seeks to demonstrate the engagement of post-extinction dopamine neurotransmission and downstream acute reorganization of dopaminergic resting-state neural networks as a means of increasing consolidation of generic fear extinction learning in adult women with PTSD.

## **B. Specific Aims**

**Specific Aim 1: Test the degree to which endogenous and exogenous manipulations of dopamine neurotransmission affect fear extinction learning across multiple indices.** *Hypothesis:* L-DOPA dose will interact with dopaminergic gene score to predict fear extinction learning across indices.

**Specific Aim 2: Test the degree to which post-extinction functional connectivity within dopaminergic neural networks mediates the effect of dopaminergic manipulation on fear extinction learning.** *Hypothesis:* The L-DOPA x dopaminergic gene score will predict enhanced post-extinction dopaminergic functional connectivity, which in turn predicts enhanced fear extinction recall.

## **C. Study Design**

*Overview.* There are three main stages to this experimental protocol: 1) Assessment, 2) Day 1 fMRI, and 3) Day 2 fMRI. Participants would complete these stages across 2-3 days, depending on participant need. Day 1 fMRI and Day 2 fMRI will always be consecutive days.

During the Assessment stage, participants would undergo a structured clinical interview to assess trauma history and mental health diagnoses (See Assessments Section). The assessment stage lasts 3-4 hours.

During Day 1 fMRI, participants would complete ~40 min fMRI scan, then ingest a pill (placebo, 100mg L-DOPA, or 200 mg L-DOPA) upon leaving the scanner and wait in a waiting room for ~45 minutes. Participants then complete the Side Effect Checklist to assess for any drug-related side effects. The participant would then undergo a 7 min resting-state fMRI scan, which concludes Day 1 fMRI. Day 2 fMRI lasts about 2 hours.

Participants return ~24 hours later for Day 2 fMRI, in which they first complete the Side Effect Checklist again and then complete a single ~40 minue fMRI scan. Day 2 fMRI lasts about 1 hour.

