### Study Population

*Participant recruitment.* Participants will include 105 women aged 21-50. In order to achieve these enrollment goals, up to 260 adults could be recruited and screened for eligibility. Participants will be recruited primarily from the WisPIC outpatient mental health clinic where the PI maintains a clinical practice. We will also recruit through focused community networking with women's shelters and related service organizations and through community-wide general advertisements (e.g., newspaper ads, flyers, etc). We have worked with women's shelters in the past by contacting them to notify them of the study and providing brochures, which then they post in their facility. Interested participants would then contact us to learn more about the study.

*Inclusion/Exclusion Criteria.* Inclusion criteria will be 1) females age 21 – 50 years of age, 2) a current diagnosis of PTSD where the index traumatic event includes physical or sexual assault, 3) English speaking, and 4) medically healthy. Assault exposure will be defined as witnessed or directly experienced exposure to physical or sexual assault (Cisler et al. 2011; Kilpatrick et al. 2000; Kilpatrick et al. 2003; Resnick et al. 1993). To facilitate generalization to real-world populations of women with assault-related PTSD (Kessler et al. 1995; Kessler 2000), current comorbid major depressive disorder or anxiety disorders will not be exclusionary as long as the PTSD diagnosis is primary.

Exclusionary criteria include: 1) internal ferromagnetic objects (such as electronic devices, surgical implants, shrapnel, etc.), 2) major medical disorders (such as cancer), 3) ADHD, 4) psychotic disorders, 5) mental retardation, 6) developmental disorders, 7) active substance use disorders, 8) pregnancy, and 9) glaucoma. Medications will not be exclusionary, as long as the medication has been stable for at least 4 weeks and do not effect neurovascular properties upon which BOLD fMRI capitalizes (e.g., water pills). Acute sedatives / pain killers (e.g., benzodiazepines, vicodin) and prescription stimulants (e.g., Adderall) would not be permitted for 6 hours prior to the scan or for two hours after the scan. Medication prescription use will be modeled as a covariate. See below for detailed exclusion criteria.

Due to safety concerns, participants with these conditions will be ineligible to participate:

- Claustrophobia, or the inability to lie still in a confined space

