### *Clinical Trial Procedures*

L-DOPA

*Administration.* Prior to pill ingestion, participants would undergo a standardized medical exam (see attached physician screening form) with a study physician to rule out medical and pharmacological contraindications for L-DOPA prescription. Upon passing the medical exam, the study physician would write a prescription to the UW research pharmacy, who maintains the blind, to dispense to our research staff the correct pill. Participants would be randomized to receive either a placebo, 100mg (with 25 mg carbidopa to inhibit peripheral decarboxylase), or 200mg (with 50 mg carbidopa to inhibit peripheral decarboxylase) pill of L-DOPA (see below for randomization and blinding procedures).

The study drug is prepared and maintained by the research pharmacy. Medication is put into two gel capsules, which are identical across the dose ranges of placebo, 100mg and 200mg. Medication kits are prepared separately for the three groups and stored in the locked nurses office of WisPIC along with the study logs of drug administration and allocation for each subject (e.g., subject 001, allocated to group 'blue', provided dose on 2/18/17). There is no washout period required for this study, though participants are required to have been stable on previous medications for at least 4 weeks. Use of MAO-I in past two weeks is exclusionary. As noted above, physician evaluation is performed prior to prescription being written. Participants are assessed for side-effects after 40-min and again 24-hours later.

*Justification and Rationale for L-DOPA Dose Choices.* The dose of 100 mg is consistent with prior studies of L-DOPA on learning as a dose optimizing the inverted U-shaped curve for the dopamine/performance relationship, while the dose of 200 mg is chosen as a suprathreshold dose that establishes the upper bound of the inverted U curve of the dopamine/performance relationship (Monte-Silva, Liebetanz, Grundey, Paulus, & Nitsche 2010; Thirugnanasambandam, Grundey, Paulus, & Nitsche 2011). We chose 200 mg as the suprathreshold dose, as opposed to 300 mg or 500 mg, in order to keep the dose small enough to not inadvertently break the blind (i.e., higher L-DOPA doses are more likely to result in side effects such as dizziness, nausea, fatigue, etc.), and 200 mg has been successfully used in prior learning studies as a suprathreshold dose.

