*Personal health information/Loss of confidentiality.* With all research participation, there is a risk that personal information obtained from research participants will be mishandled, and confidentiality may be compromised. With the current vulnerable sample of assaulted women, an associated risk of confidentiality loss is that the abuser might learn of their participation in this study and possibly then retaliate. An additional confidentiality concern is suicidality; that is, if suicidal ideation is observed, it might be clinically indicated to break confidentiality to protect the participants. Additionally, as mandated reporters, if we learn about a situation the participant is involved pertaining to child abuse or elderly abuse, we may have to break confidentiality. Upon IRB approval, we will apply for a certificate of confidentiality.

*Side effects from acute administration of L-DOPA.* It is possible that acute administration of L-dopa can cause transient side effects, such as dizziness, nausea, headaches, and drowsiness.

*Blood draw and genetic testing.* The risks associated with the blood draw itself include discomfort or bruising at the draw site. Because genetic analysis involves information that may uniquely identify participants, there is a risk of genetic information being used to re-identify participants.

*Adequacy of protection against risks.* Procedures to minimize risks identified in the previous section are outlined below.

*Internal metal during MRI scanning.* Participants will be verbally screened several times prior to MRI scanning in order to exclude any participants with internal metal.

*Possible Peripheral Nerve Stimulation (PNS).* All pulse sequences will be conducted with specific absorption rates of <36% in order to reduce the possibility of PNS. Participants will be instructed to notify the study team if they notice any involuntary muscle contractions.

*Possible hearing damage resulting from scanner noise.* All participants will be required to wear ear plugs and noise-canceling headphones to prevent any damage to their hearing.

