*Personal health information/Loss of confidentiality.* Standard practices will be used to protect participant confidentiality and personal health information, including removing identifiers from all data collected, using only numbers to identify participant data, and keeping all data files when not in use in a locked filing cabinet behind a locked office. No names or other identifiers will be used in computerized data files.

Furthermore, some women may participate who are currently in an abusive relationship. In cases such as this, it is sometimes possible that the abuser would become angry and retaliate against the participant for disclosing the abuse. In to protect the participant against possible retaliation from the abuser, we would assess the current safety of the participant with respect to the perpetrator. This clinical assessment would be conducted a female research staff member. Depending on participant need given their unique circumstance, an individualized safety plan would be created for the participant that might include entering therapy, withdrawing participation, entering a women's shelter, contacting the police, etc.

Participants would be notified in the informed consent that confidentiality might be breached in the case of suicidal ideation in order to protect the participant's safety.

*Side effects from acute administration of L-DOPA.* To ensure the participants protection, we escort the participant to a waiting room for monitoring for ~45 minutes after drug administration. We then administer a standardized medication Side Effect Checklist to assess for any side effects that require immediate attention. Upon return to the lab 24 hours later, we re-administer the Side Effect Checklist to assess for any new side effects that require attention prior to beginning the fMRI Day 2 procedures. Participants are additionally given a 24-hour emergency contact number in case of any study-related emergencies.

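### No Side Effect Checklist is scheduled before the capsules, so symptoms already present cannot be separated from post-dose symptoms in an individual woman (minor; the placebo contrast stays unbiased)

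*Combined protocol and SAP*

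**What the plan says.** The Overview in Section C sets the Day 1 order. Participants complete the scan, "then ingest a pill (placebo, 100mg L-DOPA, or 200 mg L-DOPA) upon leaving the scanner and wait in a waiting room for ~45 minutes", and "Participants then complete the Side Effect Checklist to assess for any drug-related side effects". On Day 2 they return about 24 hours later for a session "in which they first complete the Side Effect Checklist again", before the scan.

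The L-DOPA administration text under Clinical Trial Procedures restates the schedule: "Participants are assessed for side-effects after 40-min and again 24-hours later". Both time points follow the dose, but the first is 40 minutes here and about 45 minutes in Sections C and E.

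The protections part of Section E gives a triage purpose for the first form: "We then administer a standardized medication Side Effect Checklist to assess for any side effects that require immediate attention". For the second it says "we re-administer the Side Effect Checklist to assess for any new side effects that require attention prior to beginning the fMRI Day 2 procedures".

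The potential-risks part of Section E says that acute L-DOPA "can cause transient side effects, such as dizziness, nausea, headaches, and drowsiness". The eligibility text says "Medications will not be exclusionary, as long as the medication has been stable for at least 4 weeks", subject to a condition about effects on the BOLD signal, and it admits comorbid depression and anxiety disorders.

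**The concern.** Section C ties the checklist to effects of the drug. Calling a symptom drug-related implies a comparison with the woman's state before the drug, and the schedule does not record that state on the same items.

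The symptoms in question are common and non-specific, and the protocol itself supplies other sources for them before the capsules: time in a noisy scanner, stimulation that it says may cause discomfort or pain, imaging-related distress, permitted medication, and comorbid conditions.

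What is at stake is the reading of individual checklist reports and the precision of any side-effect comparison between arms. The comparison has some scientific use. The dose rationale keeps the upper dose at 200 mg partly because side effects at higher doses might reveal the assignment, and this checklist is the only side-effect measure described that could show whether that reasoning held.

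**Working it through.** The plan states no side-effect rate and no side-effect analysis, so there is no figure to reproduce. The check has three parts.

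**1. Is there a pre-dose record anywhere in the supplied text?**

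| Place | What it provides | Before the capsules? |
|---|---|---|
| Section C, Overview | Checklist after a wait of about 45 min; again at about 24 h | No |
| Clinical Trial Procedures | Checks at 40 min and 24 h | No |
| Section E, protections | Checklist after about 45 min; again at 24 h | No |
| Self-Report Measures list | Checklist named without timing | Not stated |
| Participant assessment | Most measures done at visit 1, not itemized | Not stated |
| Clinical Trial Procedures, medical exam | Physician check for contraindications | Yes, but not described as a symptom record on matching items |

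No row schedules the checklist between the first scan and the capsules. The two untimed rows do not establish a baseline. Even a visit 1 completion would miss symptoms arising from the Day 1 scan and stimulation.

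**2. How far could individual attribution be off?** All rates here are assumptions.

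*Model A.* A share b of women has at least one listed symptom beforehand, all of these persist to the first check, and the drug adds 10 percentage points. Share of active-arm reporters who would have had a symptom anyway = b / (b + 0.10).
- b = 0.10: 0.10 / 0.20 = 50%
- b = 0.40: 0.40 / 0.50 = 80%

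*Model B.* Background b is the same in all arms, and the drug causes a symptom in 20% of women who would not otherwise have one. Active-arm rate p = b + 0.20(1 − b); non-drug share = b / p; excess over placebo = p − b. Power is for one active arm against placebo, 35 per arm, two-sided alpha 0.05, using the normal approximation for two proportions (pooled variance under the null).

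| b | p | Non-drug share | Excess over placebo | Power, 35 v 35 |
|---|---|---|---|---|
| 0.10 | 0.28 | 36% | 18 points | 48.3% |
| 0.20 | 0.36 | 56% | 16 points | 31.7% |
| 0.30 | 0.44 | 68% | 14 points | 22.5% |
| 0.50 | 0.60 | 83% | 10 points | 13.0% |

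The third column is the individual-level problem. The fourth shows that subtracting the placebo rate recovers the true excess at every b, because the background is shared across arms. The fifth shows that precision is limited.

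**3. What could a pre-dose value add in precision?** If the checklist yields a severity score (the documents do not say that it does) whose pre-dose and post-dose values correlate at r, adjustment removes a fraction r² of the variance:
- r = 0.3: 9%
- r = 0.5: 25%
- r = 0.7: 49%

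At r = 0.5, 35 women per arm would be worth about 35 / 0.75 ≈ 47 without adjustment.

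**The case against.** The strongest reply is that the design already answers the question that matters. The placebo arm is randomized and double-blind. All arms have the same scan and stimulation before the capsules, under the same entry rules, and the urn scheme balances comorbid diagnoses and medication. Background symptoms therefore do not bias the between-arm contrast. This stands.

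A reader might infer that every symptom ticked is counted as drug-related. The documents do not support that. The supplied text has no counting or attribution rule, Section G has no side-effect endpoint or tabulation, and Section D refers safety monitoring to a separate document that was not available. The physician screening form is also a separate attachment, so a symptom record there cannot be ruled out.

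A reader might also infer that consultation, emergency escort and removal depend on attributing the symptom to the drug. Section E ties these to observed symptoms, the participant's request, clinical indication, or inability to continue. The removal text does mention side effects, but its operative condition is being unable to go on. None of these requires proof of cause.

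Nor does the missing form make the 24-hour search for new effects meaningless. New can be read as new since the first post-dose form, and that comparison exists.

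Finally, a pre-dose form would not settle cause for one woman. Expectancy, delayed effects of the scan, and non-drug symptoms that start after the capsules would remain. The placebo contrast is still what identifies a drug effect. This also stands, and it limits what the change can achieve.

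What survives is narrower. Staff are blind, so the placebo arm cannot help in reading one woman's form, and pre-existing symptoms are a removable part of the ambiguity.

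**Conclusion.** The supplied text schedules no checklist before the capsules, so an individual report cannot separate symptoms already present from symptoms that began after the dose. This is a loss of information at the individual level and of precision at group level, not a bias between arms.

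Under the assumed rates, the share of active-arm reports not due to the drug runs from 50% to 80% in Model A (background 10% to 40%) and from 36% to 83% in Model B (background 10% to 50%). These figures show the possible size only, because the documents give no background rate, drug effect or correlation.

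The severity is low. Side effects are not among the Section G outcomes, and no documented decision is shown to turn on the missing form. It is still worth acting on, since the change is cheap and the pre-dose record cannot be recovered afterwards. The conclusion would weaken if the separate monitoring document or the physician form already records the same symptoms before the capsules, and particularly if it does so after the first scan.

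**What to change.** Give the existing Side Effect Checklist once more on Day 1, after the woman leaves the first scan and before she takes the capsules. At the first post-dose check and at 24 hours, report by arm the items that are new or worse than that record. State that active-versus-placebo contrasts, not individual reports, are the basis for calling an effect drug-related. If the form gives a severity score, adjust the contrast for the pre-dose value.

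Separately, reconcile the timing of the first post-dose check, which is 40 minutes under Clinical Trial Procedures and about 45 minutes in Sections C and E.

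The cost is one more completion of a form already in use, taking an assumed two minutes or so and delaying the capsules by that time. Asking beforehand may slightly prime symptom reports. The pre-dose asking is the same in every arm, but equal priming in all arms cannot be guaranteed, because women with real drug effects may be more alert to the listed items.
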